18.5 UNBLINDING

If there is a need to unblind a subject's treatment assignment for emergency medical management, the Investigator will contact the Medical Monitor. The Medical Monitor, in consultation with Sponsor, will make a decision to unblind. If the decision has been made to unblind, a prompt written or electronic notification will be provided to the Investigator.

If reporting of an AE is to be performed unblinded as per any regulatory authority's guidelines, study-unrelated Sponsor personnel will unblind the individual subject's treatment group and will perform the unblinded reporting. No treatment group information would be shared with blinded study personnel.

18.6 RANDOMIZATION AND TREATMENT ASSIGNMENT

Subjects will be randomized at a 2:1 allocation ratio to receive AMG 714 8 mg/kg or placebo a total of 7 times over 10 weeks. The randomization will not be stratified as type II RCD is rare and the number of subjects in the study is small. For dosing times see the study Schedule of Events (Table 1).

The unblinded pharmacist, or unblinded study staff designee, will be responsible for dispensing the study medication according to the treatment assignment provided by EDC.

18.7 DRUG SUPPLIES, DISPENSING, STORAGE AND ACCOUNTING

In addition to the information contained in this section of the study protocol, detailed information regarding the study drug will be provided in a separate IB, Investigational Product Manual, or equivalent document.

18.7.1 Packaging and Formulation

AMG 714 will be manufactured and packaged by Amgen and distributed using the Sponsor or Sponsor representative's clinical study drug distribution procedures.

Active clinical supply will be provided in glass vials as a frozen, clear, sterile protein solution, with a light yellow color. The vials supplied are for single-dose use only. Volume and concentration will be provided in the IB, Investigational Product Manual, or equivalent document.

18.7.2 Storage

AMG 714 must be stored in a secured $-30^{\circ}\text{C}/\pm 10^{\circ}\text{C}$ freezer, protected from light in its original packaging. Prolonged exposure to light should be avoided.

Efforts should be made to ensure that the preparation procedures and conditions are consistent.

Records of the actual storage conditions for AMG 714 and placebo during the period of the study must be maintained and recorded (e.g., daily and continuous freezer temperatures, date, time, and initials of person checking). A temperature alarm should be maintained and be used to alert site personnel of significant changes in freezer temperature. Study site staff must notify the Sponsor immediately if any clinical supply is exposed to excessive or uncontrolled temperatures so that possible replacement clinical supplies can be provided if necessary.

18.7.3 Preparation and Administration

The unblinded study staff member responsible for receiving and preparing the study medication must obtain the treatment assignment via the EDC system a minimum of 24 hours prior to the scheduled randomization visit (Visit 1; Week 0/Day 0). This will allow for proper thawing and preparation of the study drug. Each subsequent visit should be documented in the EDC system in order to assure proper drug accountability.

On the day before investigational product administration, AMG 714 must thaw overnight at 2 to 8° C. Vials must continue to be protected from light during the thawing process. Once thawed, vials should be transferred to room temperature and gently swirled to ensure mixing. Avoid vigorous shaking or vortexing. Mixing may result in the formation of small bubbles, which is normal. Preparation of the clinical supplies should be performed using aseptic techniques, under sterile conditions. Prolonged exposure to light should be avoided.

Please note that certain routine supplies and equipment will be provided by the study site, including but not limited to:

- 1) IV bags (5% dextrose)
- 2) Infusion pump
- 3) IV line

The investigational product must be diluted using the following instructions:

- 1) Withdraw the volume of the thawed investigational product needed for the weight of the patient (8 mg per kg, calculating the volume needed given the concentration of investigational product of 100 mg/ml) and inject this volume directly into a 100 mL 5% dextrose IV bag using the injection port at the base of the bag.
- 2) Gently inverse the IV bag a couple of times to ensure mixing and also ensure that there are no air bubbles remaining in the injection port.

After thawing, the product may be stored for up to 72 hours at $5 \pm 3^{\circ}\text{C}$, and no longer than 12 hours at room temperature. The prepared product (i.e., the diluted product in the IV bag) should be used immediately, and can be kept for a maximum of 12 hours at room temperature, including the administration time of 2 hours.

All prepared IV bags must be labeled prior to administration with the following information:

- Study number
- Subject identification number (001-###-###)
- Date and time of preparation
- Initials of pharmacist
- Initials of subject (if permitted by regulations)

Once mixed with the investigational product prepared IV bags will not differ in color from the IV bags containing placebo. The product must continue to be protected from light using either foil or other light protective material.

An experienced and qualified blinded study staff member must perform the placement of the IV catheter and subsequent IV administration.

On any given day, if more than one subject is scheduled to receive study drug administration at the same research facility (which can only happen after the 10th patient has been dosed, see Section 7), each dose administration must be given at least 15 minutes apart.

18.7.4 Supply and Return of Drug

At study initiation, and as needed thereafter, AMG 714 will be shipped to the assigned unblinded pharmacist or unblinded study staff member at the Investigator's institution. To maintain blinding only the assigned unblinded pharmacist or unblinded study staff member should check the amount and condition of the drug and enter these data into the drug accountability form or equivalent document. At the end of the study, or as directed by the Sponsor, all unused investigational product will be destroyed or returned. Used vials of study drug may be destroyed on site at the time of study drug preparation with preapproval from the study sponsor. Please reference the Investigational Product Manual for additional information regarding study drug destruction and return.

18.7.5 Investigational Product Accountability

An Investigational Product Accountability Record for AMG 714 must be kept current and should contain:

- The dates and quantities of investigational product received
- Manufacturing batch numbers for product received
- Subject's identification
- Date and quantity of investigational product dispensed
- The initials of the dispenser
- Dose preparation records
- Date and quantity of drug destroyed

At the end of the study, the Final Investigational Product Disposition Statement must be completed and provided to the Sponsor.

18.8 TREATMENT OF INVESTIGATIONAL PRODUCT OVERDOSE

There is no information available on the effects of an overdose of AMG 714. Given the known safety profile, no specific recommendations can be issued at this time and Investigators shall use clinical judgment to treat this potential event.

19 STOPPING CRITERIA

19.1 INTERRUPTION OF DOSING IN AN INDIVIDUAL SUBJECT

Due to the current safety profile, no specific stopping rules have been identified for individual subjects. Investigators will exercise clinical judgment to assess whether an adverse event merits discontinuation of dosing in any given subject.

Dose escalation or reduction is not allowed.

19.2 INTERRUPTION OF DOSING FOR ALL SUBJECTS IN THE ENTIRE TRIAL

If any of the following occur:

- Death of any subject
- Anaphylactic reaction in any subject
- A life-threatening adverse event in any subject

The Sponsor will ask the DSMB to review the case. The committee and Sponsor will determine if a study wide interruption in dosing is required.

20 SUBJECT COMPLETION AND WITHDRAWAL

20.1 SUBJECT COMPLETION

Subjects will be considered study completers at Visit 8 (Week 12/Day 84), regardless of whether or not the Final Study Visit (Visit 9; Week 16/Day 112) is attended.

Randomized subjects who withdraw and are not lost to follow-up will complete the study at the ET Visit.

Randomized subjects who withdraw and are considered to be lost to follow-up will complete the study at the last attended visit.

20.2 SUBJECT WITHDRAWAL

All subjects are free to withdraw from participating in this study at any time and for whatever reason, specified or unspecified, without prejudice.

Reasons for withdrawal (subjects refuse to return for any remaining study visits) or discontinuation (subjects who prematurely stop the active treatment) at any time during the study may include but are not limited to the following:

- Safety reasons, either at the discretion of the Investigator or at the subject's request. In particular, subjects will be discontinued from the study if they develop severe complications of celiac disease that require intensive treatment (EATL, perforation, etc.).
- Protocol violations at the discretion of the Sponsor.
- Subject noncompliance to study procedures or schedule
- Concomitant therapy that could interfere with the results of the study (the Investigator will report all such information on the eCRFs and decide, in accordance with the Sponsor, whether the subject is to be withdrawn).
- Subject's decision to withdraw at any time.

Subjects who withdraw prior to receiving the study drug are considered screen failures.

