1.2.2 Current Treatment of Refractory Celiac Disease

The treatment of RCD is difficult. Abnormal lymphocytes are scattered in the whole small intestinal epithelium and usually in the stomach and colon, thereby precluding surgery. Currently, there is no standard of care for RCD-I or RCD-II. In RCD-I, corticosteroid (local or systemic), azathioprine, purinethol, anti-TNF agents, or cladribine may be used with limited success (Brar *et al.*, 2007; Goerres *et al.*, 2003). In RCD-II, budesonide (Brar *et al.*, 2007), cladribine (Tack *et al.*, 2011a) and autologous bone marrow transplantation (Tack *et al.*, 2011b) have also been used with different degrees of success, and better outcomes for autologous BMT (Nijeboer *et al.*, 2015b). The prognosis of RCD-II is still poor with death occurring within 3-10 years due mainly to intractable diarrhea and/or development of high grade EATL lymphomas or, more rarely, to dissemination of the low grade proliferation to other tissues (e.g., skin, lungs). The treatment of the high grade lymphoma (EATL) relies on surgical resection and chemotherapy, but the prognosis is very poor.

An effective treatment for RCD-II that could reduce the presence of aberrant IELs and alleviate the histological abnormalities and/or the symptoms, remains the highest priority.

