20.2.1 Withdrawal Procedures

If for any reason a subject is withdrawn or discontinues before completing the final visit, the reason for termination must be recorded in the source documents and reported on the appropriate eCRF. All data gathered on the subject prior to termination will be made available to the Sponsor.

Subjects discontinuing study drug should continue to be fully evaluated per the protocol event schedule, when possible, for safety purposes. However, if the subject discontinues before

Week 6, the second biopsy will not be collected. If a discontinuation occurs on or after Week 6, the second biopsy will be obtained.

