21.5 SERIOUS ADVERSE EVENTS

An AE is serious if:

- it was fatal (i.e., the AE caused or led to death)
- it was life threatening (i.e., the AE placed the subject at immediate risk of death; an AE that hypothetically might have caused death if it were more severe is not an SAE by this criterion)
- it required or prolonged hospitalization (i.e., the AE resulted in a minimum 24 hour hospitalization or prolonged a hospitalization beyond the expected length of stay; hospital admissions for elective medical/surgical procedures, or scheduled treatments are not SAEs by this criterion)
- it resulted in permanent or significant disability/incapacity (i.e., the AE resulted in a substantial disruption of the subject's ability to carry out normal life functions)
- it resulted in a congenital anomaly/birth defect (i.e., an adverse outcome in a child or fetus of a subject exposed to the study drug prior to conception or during pregnancy)
- it required significant medical or surgical intervention to prevent permanent impairment or damage (e.g., hypotension requiring pressers to prevent ischemia, replacement of broken or malfunctioning device).

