As a secondary assessment, the same model will be fitted using the absolute change in % of aberrant IELs vs total IELs as a response variable. The modelling results (ANOVA table, parameter estimates, estimated treatment effect, marginal (i.e. least squares) means estimates and results of the check of assumptions) will be tabulated and 90% confidence intervals added, where appropriate.

A frequency table by treatment group will be used to summarize the percentage of patients who reach normalization of aberrant IEL counts by flow cytometry measured as aberrant IELs < 20% of total IEL based on the second biopsy after Week 6. Additionally, a frequency table of subjects with at least 20% reduction from baseline in the % aberrant IELs vs total IELs by treatment arm will also be created, if applicable.

The baseline and post-baseline values along with the change from baseline values (both relative and absolute) will also be described by summary statistics and tabulated by treatment group. Baseline and post baseline values will also be listed.

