8.7 Exploratory analysis

The exploratory endpoints of the study are:

- Reduction in aberrant and abnormal IELs by flow cytometry, immunohistochemistry and TcR clonality analyses (including % of patients with normalization in IELs);
- PGA and PtGA;
- Quality of Life Assessments:
 - SF-12 v. 2;
 - EQ-5D;
- Biomarkers of disease activity;
- PK, and PK/PD correlations;
- CeD PRO;
- Assessment of the gluten-free diet (iVYLISA GIP stool test and dietician consultation).

8.7.1 Reduction in aberrant and abnormal IELs by flow cytometry, immunohistochemistry and T cell receptor (TcR) clonality analyses

Aberrant IELs were narrowly defined in [Section 2](#) for the purpose of primary and secondary endpoint analysis. In addition to these aberrant IELs, found by definition in the intestinal epithelium, cells with identical characteristics can be measured in the *lamina propria* of the mucosa (“aberrant IELs in the *lamina propria*”) and -should the aberrant IELs leave the gut mucosa to spread to other tissues- in peripheral blood also (“aberrant IELs in blood”). These cells will be assessed.

In addition to the frequency of aberrant IELs, multiple markers will be studied in IELs which may identify other abnormal IELs, defined as IELs with an inflammatory (e.g., Granzyme B-positive) or otherwise abnormal phenotype or a phenotypically normal population with abnormal prevalence in blood or biopsy tissue. These phenotypes and abnormalities may also be assessed in aberrant IELs.

IEL abnormalities may be detected by several methods, such as flow cytometry, immunohistochemistry, or with TcR clonality analyses (a method to detect abnormal and also aberrant IELs by quantifying the characteristic T cell Receptor, which is monoclonal in aberrant IELs).

While aberrant IELs are pre-defined in primary and secondary endpoints based on surface and intracellular CD3 expression by flow cytometry (and CD8 expression by IHC), at this time it is not possible to predict which other populations of IELs may be abnormal and may require analysis, which will be done ad-hoc in an exploratory fashion.

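### The carry-forward rule and the responder tables ignore why a subject stopped, so a subject discontinued for EATL can be tabulated as a responder or can leave the denominator

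*Protocol*

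**What the plan says.** **Discontinuation.** Protocol 20.2 states, under safety reasons, that "subjects will be discontinued from the study if they develop severe complications of celiac disease that require intensive treatment (EATL, perforation, etc".). Protocol 20.2.1 adds: "If a discontinuation occurs on or after Week 6, the second biopsy will be obtained". Before Week 6 no second biopsy is taken.

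**Evaluability and carry-forward.** SAP 8.1, 8.2.2 and 8.2.3 make a subject who stops on or after Week 6 evaluable if the second biopsy is collected. Its values then stand in for Week 12. The reason for stopping plays no part. Subjects who stop before Week 6, or have no second biopsy, are outside the PP set.

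**Responder definitions.** SAP 8.6.1 tabulates the "percentage of patients who reach normalization of aberrant IEL counts by flow cytometry measured as aberrant IELs < 20% of total IEL" and the proportion with at least a 20% reduction. SAP 8.6.2 adds a 20% reduction for Immunological Response 2, a 30% improvement in VH:CD, any improvement in Marsh score, and Marsh 0-1. None mentions EATL or discontinuation for a complication.

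**What the biopsy samples.** Protocol 13.2 takes tissue from the second part of the duodenum and tells the endoscopist to keep away from ulcerated areas. SAP 8.7.1 allows for spread beyond the epithelium: "should the aberrant IELs leave the gut mucosa to spread to other tissues".

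**The concern.** EATL is the outcome that makes RCD-II dangerous. Protocol 13.1 justifies the aberrant-IEL endpoints by likening a fall in these cells to tumour shrinkage and by naming them as the source of progression to EATL. A responder table that can list a subject with overt lymphoma as a success works against that rationale.

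Two errors are possible. A progressor with a favourable duodenal reading enters the numerator. A progressor without an evaluable second biopsy leaves the denominator, which raises the rate among those who remain. With planned arms of 16 and 8, one subject is visible in any percentage. If the question is first settled after unblinding, the choice will look selective whichever way it goes.

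**Working it through.** **1. Planned denominators.** Inputs from Protocol 22.1 and SAP 7: difference 20, SD 17.4, two-sided alpha 0.10, allocation 2:1. With 16 and 8 subjects the noncentrality is 20 / (17.4 × √(1/16 + 1/8)) = 2.654 on 22 df, which gives 82.3% power. The stated figure of at least about 80% with 24 subjects is reproduced, and nothing below alters it. The arms of 16 and 8 are used from here on.

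**2. What the rules do with a subject discontinued for EATL.**

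| Situation | Result under the documents |
|---|---|
| Stops before Week 6 | Out of PP; not a failure |
| Stops on or after Week 6, no second biopsy | Non-evaluable, out of PP; not a failure |
| Excluded for prohibited medication or another procedure (SAP 8.1, by judgement) | Out of PP; not a failure |
| Stops on or after Week 6, biopsy taken, in PP, unfavourable reading | Non-responder, because of the biopsy |
| Stops on or after Week 6, biopsy taken, in PP, favourable reading | Responder |

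In no row does the progression itself decide the classification.

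**3. Which tables are exposed.** Table 2 in Protocol 1.2.1 lists EATL with more than 20% aberrant IELs. If that holds in the sampled duodenum, a progressor fails the below-20% definition. It does not prevent a fall of at least 20% from baseline, a VH:CD gain of at least 30%, or a better Marsh class.

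**4. Effect of one subject.** A wrongly counted responder moves a rate by 1/16 = 6.25 points on AMG 714 or 1/8 = 12.5 points on placebo. With assumed counts of 8/16 against 1/8, the difference is 50.0 − 12.5 = 37.5 points. Rescoring one AMG 714 responder gives 7/16 against 1/8, or 43.75 − 12.5 = 31.25 points. If a subject who progressed before Week 6 is dropped instead of counted as a failure, 8/16 (50.0%) becomes 8/15 (53.3%).

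**5. How likely a progression is.** Protocol 1.1 gives about 50% progression without a time horizon. Assumption: constant hazard, with 50% reached after T = 3, 5 or 10 years. The 3 to 10 years is the range that Protocol 1.2.2 gives for time to death, borrowed here only to set a scale. Six-week risk = 1 − 0.5^((6/52)/T). Chance of at least one case = 1 − (1 − risk)^24, taking all 24 subjects as at risk at Week 6.

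| T (years) | Six-week risk | Expected in 24 | At least one in 24 |
|---|---|---|---|
| 3 | 2.63% | 0.63 | 47% |
| 5 | 1.59% | 0.38 | 32% |
| 10 | 0.80% | 0.19 | 17% |

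This is the chance of a progression in the window where carry-forward applies. The chance of a misclassified responder is smaller, because it also needs a biopsy, PP inclusion and a favourable reading. The documents give no figures for those steps.

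**The case against.** **The exit biopsy is not automatic.** Footnote 5 of Table 1 and Protocol 11.4 let the investigator omit the endoscopy because of the subject's condition, and a perforation or lymphoma is an obvious reason to do so. SAP 8.1 may also remove a treated progressor from PP. A reader might infer that every subject who stops for EATL after Week 6 ends up as a responder; the documents do not support that. The omitted or excluded subject is still not a failure.

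**The tables are not decisive.** The primary analysis is an ANCOVA on a continuous change, and the Go/No-Go rule in Protocol 13.1 rests on the two Immunological Responses. Most of the responder summaries are frequency tables without a test; the exception is Marsh improvement, which is the modelled response in a logistic regression. Reasons for discontinuation are tabulated by arm, adverse events leading to discontinuation receive narratives (SAP 8.8.1), and imaging results are listed. An attentive reader could find the progressor. This limits the weight of the point, but the responder percentages would still be wrong.

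**Safety reporting.** A reader might infer that EATL escapes the SAE rules and will be reported late. Protocol 1.2.2 says "The treatment of the high grade lymphoma (EATL) relies on surgical resection and chemotherapy", and 21.5 says "hospital admissions for elective medical/surgical procedures, or scheduled treatments are not SAEs by this criterion". That exemption is confined to the hospitalization criterion. Section 21.5 separately covers an event where "it required significant medical or surgical intervention to prevent permanent impairment or damage". Section 21.6.2 makes the event behind a hospitalization for a surgical or diagnostic procedure the SAE, 21.7 requires a record of new signs or symptoms or an atypical course, and 21.10 gives the DSMB access to all data as the study runs. Most EATL would probably be captured. What remains is narrow: neither 21.5 nor 21.6 names EATL, so a case managed without hospitalization depends on the site's judgement.

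**Conclusion.** The point holds for the supportive efficacy tables. Carry-forward that ignores the reason for stopping, combined with responder definitions that are silent on progression, allows a subject discontinued for EATL or another severe complication on or after Week 6 to be counted as a responder. The 20% reduction, VH:CD and Marsh tables are the most exposed. Earlier progressors and those without a second biopsy disappear from the rates.

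One subject is worth 6.3 or 12.5 points, and the direction of the bias depends on the arm. The 47% to 17% range rests wholly on the assumed constant hazard and horizon, and it is an upper limit for misclassification under those assumptions. The sample size, power and form of the primary analysis are unaffected. Late reporting of EATL is not established; on safety, only a clarification of wording is warranted.

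**What to change.** **SAP 8.6.1 and 8.6.2.** Add that a subject with EATL, or discontinued under Protocol 20.2 for a severe complication of celiac disease, is a non-responder in the responder tables (aberrant-IEL normalisation, 20% reduction for Immunological Response 1 and 2, VH:CD and Marsh) whatever the biopsy shows. Keep such subjects in the denominator even if they stopped before Week 6 or have no second biopsy. State the date up to which a diagnosis counts. Show the number of these subjects by arm beside the primary result, since the same carried-forward biopsies enter the ANCOVA.

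**Protocol 21.5 or 21.6 (minor clarification).** Name EATL or any new malignancy as an event reported under 21.8, so that classification does not depend on how the case is managed.

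**Cost.** A few sentences. Responder rates may be slightly less favourable, and the denominator of these tables may differ from the PP count, which needs a footnote. No extra data collection is needed, because reasons for discontinuation are already recorded.
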